1.4 Compliance Statement

This study will be conducted in full accordance all applicable Children's Hospital of Philadelphia Research Policies and Procedures and all applicable Federal and state laws and regulations including 45 CFR 46. All episodes of noncompliance will be documented.

The investigators will perform the study in accordance with this protocol, will obtain consent and assent, and will report unanticipated problems involving risks to subjects or others in accordance with The Children's Hospital of Philadelphia IRB Policies and Procedures and all federal requirements. Collection, recording, and reporting of data will be accurate and will ensure the privacy, health, and welfare of research subjects during and after the study.

2 STUDY OBJECTIVES

The purpose of the study is to assess the acceptability and feasibility of a novel intervention to improve sleep in the hospital setting, which will provide evidence for a clinical intervention that can improve patient functioning during hospitalizations.

2.1 Primary Objective (or Aim)

The primary aim of the study is to assess the feasibility and acceptability of increasing time between vitals checks in HSCT.

2.2 Secondary Objectives (or Aim)

The secondary objectives are to:

Test the relationship between increasing time between vital checks and sleep.

Compare engagement in supportive care interventions (PT/OT/School/Creative Arts Therapy/Psychology), HRQL, and symptom burden between observation and intervention periods.

3 INVESTIGATIONAL PLAN

3.1 General Schema of Study Design

Patients undergoing HSCT face many challenges to restful sleep during the hospitalization for transplant. Frequent vitals checks, necessary during conditioning and immediately post-transplant, may be less necessary as time from transplant increases. Utilizing an aggregated N=1 randomized trial design (Figure 1. Study Flow), the current study will test protecting one 6-hour window for sleep within patients recovering from HSCT. This study will assess the acceptability and feasibility of this intervention, evaluate the impact on patient sleep, and test how sleep is related to symptom burden, engagement in supportive services, and HRQL during HSCT recovery. Participants will wear an actigraph for the duration of the study (day of the transplant [day 0] through the night of Day +14post-transplant, removing the actigraph upon awakening on Day +15) to measure sleep accompanied by a brief sleep diary sent daily by text messages delivered via REDCap and its integration with Twilio.

Participants will complete self-report measures of sleep, symptom burden, and HSCT related

HRQL at baseline and at the end of each study period (Day +5, +10, +15; Table 1 Study Procedures).

3.1.1 Screening Phase

Potential subjects will be identified through the Stem Cell Transplant List using inclusion criteria for enrollment: ages 8-21, receiving HSCT at CHOP, English speaking, with no history of developmental delays. Subjects will be recruited into two strata, children ages 8-12 years and adolescents and young adults ages 13-21 years.

Parental/guardian permission (informed consent) and, if applicable, child assent, will be obtained prior to any study-related procedures being performed. Eligibility criteria will be confirmed by the subject's oncologist. Participants will be approached about study participation on transplant education day or during the conditioning admission, if interested the study team will follow up with the family 1-2 days before the transplant to complete the informed consent process and the baseline measures.

3.1.2 Study Treatment Phase (start of the study intervention)

One-two days before the transplant, a study team member will meet with the family to complete the informed consent, baseline measures, and give actigraphy instructions. All patients will wear an actigraph from the day of the transplant until day +5 from the transplant to serve as the “observation baseline” for each patient.

3.1.3 Phase 2

On Day +5, to reduce the impact of expectancies during the first observation period, patients will be randomized to ABA (observation/intervention/observation) or AAB (observation/observation/intervention), with each period lasting 5 days (Fig. 1). Block randomization stratified by age will be used to ensure similar age distribution between groups. The two group design will allow for the comparison of altering vitals checks before/after engraftment and peak symptom burden (typically on day +10⁴). On each intervention night, the research team will verify with the child's provider that it is acceptable for the patient to have a 6-hour window between vitals checks. This confirmation will be communicated to the child's nighttime nurse. For the 5 days of the child's intervention period, the nurse will be instructed to conduct the last vitals check between 9pm-1am. After the last vitals check, the patient will be given 6 hours until the next vitals check, unless the caregiver/patient request nursing. Patients will continue to wear the actigraph until the end of the study. The patient can remove the actigraph upon awakening on Day +15.

Eligibility for extended vitals check, assessed daily: 1) No fever in the last 24 hours; 2) No concurrent chemotherapy administration; 3) No ongoing or active infection; and 4) No organ toxicity requiring labs more than every 6 hours. Even if a patient is ineligible for extended vitals checks they are asked to continue to wear the actigraph.

After each patient has completed both the intervention and a second observation (either BA or AB), they will be asked to complete final study measures and measures of acceptability of the intervention.

3.2 Allocation to Treatment Groups and Blinding

Participants will be randomized to either Observation/Intervention or Intervention/Observation on day +5 post-transplant. The research coordinator will generate a randomization sequence using a random number generator, with block randomization occurring based on participant age (8-12 or 13-21). Blinding will not be possible, but randomization will occur on day +5 to minimize the impact of the intervention on the initial observation period.

3.3 Study Duration, Enrollment and Number of Sites

3.3.1 Duration of Study Participation

The study duration per subject will be up to approximately 17 days, from the beginning of data collection (the day before the transplant), up to 5 days Phase 1 and up to 10 days Phase 2.

3.3.2 Total Number of Study Sites/Total Number of Subjects Projected

The study will only be conducted at The Children's Hospital of Philadelphia.

Recruitment will stop when approximately 55 subjects and their parent caregivers are enrolled. It is expected that approximately 55 subjects will be enrolled to produce 50 evaluable subjects. Subject nurses will also be enrolled, it is expected that each subject may have between 1 and 5 nurses involved in care during the extended vitals check period, Because some nurses will likely provide care to multiple patients, we expect to enroll 75 nurses.

3.4 Study Population

3.4.1 Inclusion Criteria

(Patient Subjects)

- 1) Males or females age 8 to 21 years.
- 2) Undergoing HSCT at The Children's Hospital of Philadelphia
- 3) Parent/guardian permission (informed consent) and if appropriate, child assent.

(Nurse Subjects)

- 4) HSCT Nurse working night shift during subject's extended vitals check.

3.4.2 Exclusion Criteria

- 1) History of developmental delays given the relationship to sleep/wake patterns
- 2) Sleep disorder diagnosis as documented in the medical record
- 3) Cognitive delays that impact the ability to complete study measures
- 4) Not proficient in English

Subjects that do not meet all of the enrollment criteria may not be enrolled. Any violations of these criteria must be reported in accordance with IRB Policies and Procedures.

4 STUDY PROCEDURES

4.1 Screening Visit

- Patients and families will be presented the study on Family Education Day prior to admission for HSCT

4.2 Study Treatment Phase

General overview of this phase.

4.2.1 Visit 1 Day -2 to Day -1 before transplant

- Informed Consent
- Medical Record Review
- Demographic, COVID-19 Impact measure, and Psychosocial Measures (Symptom Burden, HRQL, and Sleep)
- Introduce actigraph and electronic sleep diary.

4.2.2 Visit 2 Day 0

- Place actigraph on patient's non-dominant wrist. Patient is asked to wear the actigraph for the duration of the study (morning of Day 0- the night of Day +14). The patient can remove the actigraph upon awakening on Day +15.
- Review actigraph and electronic sleep diary procedures.

4.2.3 Visit 3 Day +5

- Randomization
- Psychosocial Measures (Symptom Burden, HRQL, and Sleep)

4.2.4 Visit 4 Day +10

- Psychosocial Measures

4.2.5 Visit 5 Day +15

- Psychosocial Measures
- Return Actigraph
- Acceptability survey
- Subject payment

4.2.6 Nurse Study Procedure

Visit 1 Morning after patient completes extended vitals check night
Informed Consent, will take place either by phone or on the HSCT Unit with study staff
Acceptability Survey

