9.2 Data Collection and Management

Electronic health record data.

Investigators will generate a list of MRNs for participants with positive parental consent who have completed the survey. A trained research assistant with limited EHR access will extract treatment related data from the EHR. To obtain a password for the EHRs, all staff must complete training on the importance of patient privacy. Training on the Health Insurance Portability and Accountability Act (HIPAA) is required for all employees. With the EHRs, patient privacy is protected by multi-step, system wide processes. Anyone

wishing to view the charts of patients for whom they do not provide care must “break the glass.” This system requires a declaration of why the chart is being viewed and sends a message to both an employee’s supervisor and the hospital’s privacy officer. In summary, the inappropriate access to electronic health information is carefully monitored and strictly prohibited. All study files retained on CHOP’s secure network or within secure REDCap database will be accessed only by study staff using a CHOP issued, password-protected computer.

Child- and parent-report data:

Participants will complete daily sleep diary questions using REDCap and the integration with Twilio (a text messaging platform that integrates with REDCap). No PHI will be transmitted over text message. Electronic demographic, psychosocial, and acceptability surveys will also be obtained using REDCap. The CHOP Research Institute Center for Biomedical Informatics (CBMi) will be used as a central location for data processing and management. These data will be stored within REDCap by participant study ID.

Nurse acceptability data:

Nurses will complete acceptability questionnaires for each night they care for the child during the extended vitals check portion of the study using REDCap and the integration with Twilio (a text messaging platform that integrates with REDCap). No PHI will be transmitted over text message. The CHOP Research Institute Center for Biomedical Informatics (CBMi) will be used as a central location for data processing and management. These data will be stored within REDCap by participant study ID.

Confidentiality of On-Line Assessment.

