9.6 Informed Consent/Accent and HIPAA Authorization

Consent/assent for all participants will take place in person on the Stem Cell Transplant Unit at CHOP. Patients who are interested in participating will provide written consent (parents/legal guardians of children < 18 years old and AYA \geq 18 years) and assent (children < 18 years of age). A study team member will review the informed consent document with prospective participants and caregivers and answer any questions about study procedures. Separate consent forms will be reviewed and signed by patients and their caregivers, as needed. HIPAA Authorization will be obtained through a combined consent-authorization document.

Nurse Consent Plan: After subjects have completed study participation, all nurses who were involved in the subject's care during the extended vitals check period (either nights of days 5-9 or 10-14) will be contacted to invite study participation. Consent will take place on the Stem Cell Transplant Unit at CHOP or by phone prior to asking the nurse to complete the study acceptability measure. Written consent will be obtained from nurse subjects enrolled in person on the Stem Cell Transplant Unit at CHOP, while verbal consent will be obtained from nurse subjects enrolled via phone.

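### The nurses who rate acceptability are defined in two ways, one of which can depend on whether the 6-hour gap was completed, and the timing of their survey also conflicts

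*Combined protocol and SAP*

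**What the plan says.** Section 6.1 makes acceptability part of the primary endpoint, rated by patients, caregivers and nurses. Section 6.3.2 plans descriptive statistics only, with no threshold, test or unit of analysis.

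Two places attach the nurse to the check itself. The nurse inclusion criterion in Section 3.4.1 is "HSCT Nurse working night shift during subject's extended vitals check". Section 4.2.6 schedules consent and survey for "Visit 1 Morning after patient completes extended vitals check night". Section 3.4.2 makes the criteria binding: "Subjects that do not meet all of the enrollment criteria may not be enrolled".

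Three places attach the nurse to the assigned period. Section 3.3.2 expects that "each subject may have between 1 and 5 nurses involved in care during the extended vitals check period". Section 9.2 states "Nurses will complete acceptability questionnaires for each night they care for the child during the extended vitals check portion of the study". Section 9.6 says that nurses involved in "care during the extended vitals check period (either nights of days 5-9 or 10-14) will be contacted to invite study participation".

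On timing, Section 4.2.6 points to the following morning and Section 9.2 to a questionnaire for each night. Section 9.6 begins its invitation rule with "After subjects have completed study participation, all nurses who were involved in the subject's care". The measures table in Section 5.1.2 marks acceptability, including the nurse's, at Day +15.

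**The concern.** Nights in the intervention period can pass without a completed gap, and the two wordings treat the nurses of those nights differently. If entry depends on the gap having been completed, raters are selected on delivery of the thing they rate. Nurses who saw it work are heard, and nurses who only saw it fail or be called off are not. If the two groups differ in opinion, reported acceptability is too high.

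The period wording has the opposite weakness. It also collects ratings for nights on which the child was not cleared and no extension was offered.

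Site staff cannot tell from the text whom to invite, when, or how many times. Two coordinators following different sections would collect different data for the same endpoint.

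**Working it through.** **1. The passages side by side**

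| Section | What brings a nurse in | Nurse whose only night had no completed gap | When asked | How often |
|---|---|---|---|---|
| 3.3.2 | care during the period | counted | not stated | not stated |
| 3.4.1 | night shift during the child's extended check | out if no check was extended; arguable if it was started and cut short | not stated | not stated |
| 4.2.6 | a night the patient completes | out, read literally | next morning | one visit listed |
| 9.2 | each night of care in that portion of the study | in | per night | once per night |
| 9.6 | care in the assigned five nights | in | after the child has finished | one measure mentioned |

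**2. Do such nights occur?** Yes, by design. Section 3.1.3 reassesses four medical conditions every day. Sections 3.1.3 and 7.1 let the patient or caregiver call the nurse during the window. Section 6.1 tracks compliance as a feasibility outcome. The two wordings can therefore give different raters.

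**3. The plan's own figure.** Section 3.3.2 expects 75 nurses. With 55 children and 1 to 5 nurses each there are 55 × 1 = 55 to 55 × 5 = 275 nurse-child pairs (50 to 250 for the 50 evaluable children). The documents do not say how many children each nurse covers, so 75 can be neither confirmed nor refuted. It does not show which nurses count. Section 6.4 speaks of 16 subjects; the counts here use Section 3.3.2, where the nurse figure stands.

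**4. Possible size of the selection effect.** Let q be the share of raters left out, a the proportion of those kept who rate the change acceptable, and b the proportion of those left out. Then:

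- all raters = (1 − q)a + qb
- overstatement = a − all raters = q(a − b)

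The documents give none of these values. Assuming a = 85%:

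| q | All raters, b = 40% | Overstatement | All raters, b = 60% | Overstatement |
|---|---|---|---|---|
| 10% | 80.5% | 4.5 points | 82.5% | 2.5 points |
| 20% | 76.0% | 9.0 points | 80.0% | 5.0 points |
| 30% | 71.5% | 13.5 points | 77.5% | 7.5 points |
| 40% | 67.0% | 18.0 points | 75.0% | 10.0 points |

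If b = a, the overstatement is zero at every q.

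**5. q is not the share of nights.** A nurse with one completed night enters even under the strict wording. There are at most 50 × 5 = 250 nights, so up to 250/75 = 3.3 per nurse if one nurse covers each night. Suppose 20% of nights are not completed. A nurse with one night is left out with probability 20%. A nurse with three independent nights is left out with probability 0.2³ = 0.8%. With a − b = 45 points, the overstatement is 0.20 × 45 = 9.0 points in the first case and 0.008 × 45 = 0.4 points in the second. Clustering of missed nights would put a three-night nurse somewhere between.

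**6. Timing.** Take Day +15 as the earliest date under Section 9.6. Nights +5 to +9 end on the mornings of Days +6 to +10, so the delay is at least 15 − 10 = 5 to 15 − 6 = 9 days. Nights +10 to +14 end on Days +11 to +15, so it is at least 0 to 4 days. Recall would differ by randomised sequence. Under Section 4.2.6 it would not.

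**7. Repeat ratings.** Under Section 9.2 a nurse who covers all five nights of one child contributes five ratings, and a nurse who covers one night contributes one. Section 6.3.2 does not say whether nights or nurses are summarised.

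**The case against.** The best defence is that the conflict is loose drafting. No section says that nurses qualify only for completed nights. The wording in Section 3.4.1 may be shorthand for the period that Section 9.6 spells out, and in Section 4.2.6 completing a night may mean only that the night is over. Section 9.6 is the most specific recruitment text and invites everyone. On that reading nobody is excluded on outcome. This is a fair reading and rules out stating the exclusion as fact. It does not remove the inconsistency, because Section 3.4.1 is the binding criterion and nothing says which text governs.

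A reader might infer that the plan shuts out nurses who would not cooperate. The documents do not support that. The provider confirms each night, the nurse is instructed, and the stated reasons for no gap or a broken one are medical ineligibility and a patient or caregiver request.

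A reader might also infer that repeat ratings cannot be linked to nurses, because Section 9.2 stores them under a participant study ID. Nurses are themselves consented as subjects, and Section 9.2 says respondents receive a unique study ID at recruitment, so that ID may be the nurse's own. What stands is that no link between nurse and child is described.

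Two further points limit the concern. Compliance is taken separately from the health record, so missed gaps will be visible, although not what the nurse thought of them. And because the summary is purely descriptive, a variance inflation from repeat ratings has little bearing; the open question is weighting. The survey items are in Appendix B, which is not reproduced, so they may already record delivery.

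**Conclusion.** The point holds as an inconsistency in a component of the primary endpoint. The rater population is worded in two ways, and the time and number of surveys in at least three. The upward bias is possible, not shown. It requires that staff follow the literal wording of Sections 3.4.1 and 4.2.6, that some nurses have no completed night at all, and that those nurses rate the change lower.

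Its size cannot be estimated from the documents. The 0 to 18 points above rest entirely on assumed values, and the upper end needs 40% of raters to be left out. Nurses who cover several nights would bring it down, possibly to a fraction of a point. The actigraphy and supportive-care analyses are not affected. The change is worth making because it is nearly free and settles what the nurse figure describes.

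**What to change.** Use one entry rule in Sections 3.4.1, 4.2.6, 9.2 and 9.6 that does not depend on whether the gap was completed: invite the night nurse for every intervention-period night on which the child was cleared. Nights without clearance are then not rated. Restricting to cleared nights is a choice, made so that each rating refers to a night on which the extension was on offer.

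State one survey time and frequency, and align the nurse entry in the Section 5.1.2 table with it. Asking on the next morning would keep the recall delay equal in the two sequences.

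For each rated night, record whether the gap was completed and, if not, why. Report nurse acceptability overall and by delivery status.

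Confirm that each rating carries both a nurse ID and the child's ID. Give a per-nurse summary, for example the mean of each nurse's ratings, beside the per-night summary.

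The cost is wording in four sections, a table entry and a few data fields. There may be a few more invitations, and the reported rating may be less favourable. Clinical care does not change.

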4.3 Unscheduled Visits

Subjects will be hospitalized for the duration of the study. Should the family or the treatment team have concerns about the subject's participation or study procedures, the study team will meet with the patient to discuss whether the family would like to remain in the study.

4.4 Subject Completion/Withdrawal

Subjects may withdraw from the study at any time without prejudice to their care. They may also be discontinued from the study at the discretion of the Investigator for lack of adherence to study treatment or visit schedules, AEs, or due to a change in medical status. The Investigators may also withdraw subjects who violate the study plan, or to protect the subject for reasons of safety or for administrative reasons. It will be documented whether or not each subject completes the clinical study. If the Investigators become aware of any serious, related adverse events after the subject completes or withdraws from the study, they will be recorded in the source documents and on the CRF.

4.4.1 Early Termination Study Visit

Subjects who withdraw from the study will be asked to return the actigraph and complete the acceptability measure.

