5.1.2 Other Evaluations, Measures

Subjects and caregivers will complete the following measures:

| Table 1. Study Measures. | | Baseline | Day +5 | Day +10 | Day +15 |
|--------------------------|--|----------|--------|---------|---------|
| Construct | Measure | | | | |
| Acceptability | Patient, caregiver, and nurse will respond to a brief questionnaire of acceptability of adjusting vitals checks. | | | | x |
| Demographics | Report of sex, race/ethnicity, age of child and caregiver | x | | | |
| COVID-19 Impact | COVID-19 Exposure and Family Impact Survey (CEFIS) to assess family exposure to and experience with COVID-19 through Yes/No responses (25 items); 12 items assessing the impact of the pandemic on | x | | | |

| | | | | | |
|---------------------------|---|---|---|---|---|
| | self/family with 1-4 intensity scale and 1 open-ended item | | | | |
| HRQL and related symptoms | Pediatric Quality of Life Inventory—Stem Cell Transplant Module. This measure assesses HRQL and symptoms relevant to patients undergoing HSCT. The measure includes questions about pain, fatigue/sleep, nausea, communication, worry, nutrition, thinking and other symptoms answered on parallel child and adolescent with parent proxy forms (41 items). ²⁶ | x | x | x | x |
| Sleep | PROMIS Sleep Measures—Sleep disturbance, sleep-related impairment, and sleep hygiene over the past week-parallel parent/child forms (24 items) ²⁷ . | x | x | x | x |
| Supportive Care Use | EHR review to document engagement or refusal of PT/OT/School/Creative Art Therapy/ Psychology for each 5 day period. | | x | x | x |
| Actigraphy | Worn by participant day 0-night of Day +14, removing on awakening on Day+15. To validate actigraphy: bedtime, waketime, night awakenings, naps, time actigraph was off reported daily through text messages delivered via REDCap and its integration with Twilio. | | | | |

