6 STATISTICAL CONSIDERATIONS

6.1 Primary Endpoint

The primary endpoint is the acceptability and feasibility of the intervention. Acceptability will be measured by subjects, caregivers, and nursing ratings of the intervention. Feasibility will be measured through study staff documented medical eligibility to participate in the intervention each eligible day and by tracking compliance with extended vitals checks, through electronic health record (EHR) review.

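### The early-termination rule asks only the withdrawing child to rate acceptability, so caregiver ratings, part of the primary endpoint, come from completers only; the timing of nurse ratings is stated inconsistently

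*Combined protocol and SAP*

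**What the plan says.** Section 6.1 defines the acceptability part of the primary endpoint: "Acceptability will be measured by subjects, caregivers, and nursing ratings of the intervention". The measures table in 5.1.2 repeats the three groups, "Patient, caregiver, and nurse will respond to a brief questionnaire of acceptability of adjusting vitals checks", and marks that questionnaire at Day +15 only. Section 3.1.3 ties the end-of-study forms, including acceptability, to finishing both later periods: "After each patient has completed both the intervention and a second observation (either BA or AB), they will be asked to complete final study measures".

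For families who leave early, the only instruction is in 4.4.1: "Subjects who withdraw from the study will be asked to return the actigraph and complete the acceptability measure". Section 4.4 also lets the investigator discontinue a subject. Section 4.4.1 does not say whether it covers that case.

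For nurses, the consent plan in 9.6 sets contact as follows: "After subjects have completed study participation, all nurses who were involved in the subject's care during the extended vitals check period" are invited. Section 4.2.6 instead places nurse consent and survey on the morning after an extended-check night, and 9.2 has nurses answer for each such night of care.

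Section 6.3.2 analyses acceptability with descriptive statistics and gives no rule for missing ratings.

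**The concern.** Families who leave after experiencing the longer gap between vitals checks have something to say about its acceptability, and the protocol already accepts this by asking the withdrawing child. It does not ask the caregiver. Yet parents consent for minors (9.6), 4.3 frames a decision to leave as the family's, and 9.4.2 acknowledges that a fever could go undetected for up to two more hours. If caregivers of leavers are less favourable than those of completers, the caregiver result is too high. The child result would include leavers and the caregiver result would not, so the two would describe different sets of families. Nothing in 6.3.2 would reveal or correct this.

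**Working it through.** **Step 1. Does 'subjects' in 4.4.1 include caregivers?** The sentence asks the same people to return the actigraph, which 4.2.2 places on the patient's wrist. Elsewhere the protocol lists the two groups separately:
- 3.3.2: "Recruitment will stop when approximately 55 subjects and their parent caregivers are enrolled"
- 5.1.2: "Subjects and caregivers will complete the following measures"
- 9.7.1: separate payments for subjects and caregivers.

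The natural reading of 4.4.1 is the child alone. No other section gives the caregiver of a child who leaves early a route to rate.

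**Step 2. Who is lost?** The caregiver is lost if the child leaves after the first extended night and before Day +15.
- ABA: extended nights are +5 to +9, so the interval runs from night +5 to Day +15, about 15 − 5 = 10 days. About half of it falls after the intervention has ended.
- AAB: extended nights are +10 to +14, so the interval is about 15 − 10 = 5 days, with no observation period after exposure.

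The opportunity for loss therefore differs by sequence.

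**Step 3. Do nurses have a route?**
- 4.2.6: morning after an extended night, so before any later withdrawal.
- 9.2: each night of care, so also before a later withdrawal.
- 5.1.2 table: Day +15.
- 9.6: after participation is completed. This excludes leavers if 'completed' is contrasted with 'withdrawn', as 4.4 does, but not if it means that participation has ended for any reason.

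This is a conflict on timing. Loss of nurse ratings follows only from one reading of 9.6.

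**Step 4. What do the plan's own numbers imply?** Section 3.3.2 expects that "approximately 55 subjects will be enrolled to produce 50 evaluable subjects". The implied loss is (55 − 50)/55 = 5/55 = 9.1%. No dropout rate is stated and 'evaluable' is not defined, so 55 cannot be derived from a stated input. Five is an upper illustration of exposed leavers, not a planned count.

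**Step 5. Size of the effect on the caregiver figure.** Let m exposed leavers be unrated, with 50 completers rated. Completers' acceptability is c and leavers' is l.

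Overstatement = [m/(50 + m)] × (c − l)

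With the assumed c = 80% and l = 20%:
- m = 1: (1/51) × 60 = 1.2 points
- m = 2: (2/52) × 60 = 2.3 points
- m = 5: (5/55) × 60 = 5.5 points. As a check, (50 × 0.80 + 5 × 0.20)/55 = 41/55 = 74.5%, against 80% reported.

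For m = 5, with c from 70% to 90% and l from 0% to 50%, the range runs from (5/55) × (70 − 50) = 1.8 points to (5/55) × (90 − 0) = 8.2 points.

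The bounds without assuming l, for an observed 40/50 = 80% and m = 5, are 40/55 = 72.7% if all five are negative and 45/55 = 81.8% if all five are positive.

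For scale, the standard error of 80% on 50 raters is √(0.8 × 0.2/50) = 5.7 points.

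**The case against.** The best defence of 4.4.1 is that the protocol is loose about raters throughout. Section 3.1.3 speaks only of the patient completing the acceptability measure, and the Day +15 entry in the schedule of procedures lists it among self-report measures. Read literally, these would exclude caregivers at Day +15 too, yet the measures table plainly includes them. Section 4.4.1 refers to the same measure, so the caregiver may be intended. This shows that the omission may be a drafting slip. It does not remove it: the table supplies caregivers for Day +15 only, and staff following 4.4.1 would have no instruction to ask them.

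A reader might infer three stronger points that the documents do not support.
- *Nurses are lost as well, so two of the three rater groups lose leavers.* Sections 4.2.6 and 9.2 give nurses a route before any later withdrawal, so this is not established.
- *Leavers' caregivers are the negative ones, so upward bias is certain.* Section 4.4 lists adherence, adverse events, medical status, safety and administrative reasons for discontinuation, and a caregiver can ask for nursing during the window without leaving the study (7.1). Upward bias is plausible, but the documents do not show it.
- *Five of 55 will be exposed leavers.* Some non-evaluable children may leave before any extended night, especially in AAB, or be medically ineligible on the nights concerned.

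It is also true that acceptability has no threshold or test and that no comparison between rater groups is planned. That limits the consequence, but caregiver acceptability remains a reported part of the primary endpoint.

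**Conclusion.** The caregiver gap holds on the text. A primary-endpoint rater group has no stated rating when a child leaves after exposure, so its result would describe completers. The effect is modest and its size unknown: about 1.2 to 5.5 points under the assumed 80% and 20% rates with one to five exposed leavers, and below one standard error even at five. It would be zero if leavers' caregivers rate as completers' do, and reversed if they rate higher. These figures take 50 completers from 3.3.2. Section 6.4 speaks of 16 subjects, a separate discrepancy; on that number a single exposed leaver among 16 would shift the result by (1/16) × 60 = 3.8 points.

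For nurses, the finding is an internal inconsistency on timing and not a demonstrated loss of ratings. The change is worth making because it is cheap and affects what is collected for the primary endpoint.

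**What to change.** 1. In 4.4.1, ask both the child and the caregiver for the acceptability measure at early termination when the child had at least one extended-check night. State that this covers investigator discontinuation as well as withdrawal.
2. Reconcile 4.2.6, 9.2, 9.6 and the measures table in 5.1.2 on when nurses are approached and rate, so that nurses of children who leave early are included. Do not add a separate nurse form at withdrawal, which would duplicate the per-night ratings in 9.2.
3. In 6.3.2, report for each rater group the number of ratings obtained out of the number exposed, with leavers included.

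The cost is a sentence or so in each section and a few extra brief questionnaires. Some leavers will refuse, and reported acceptability may come out slightly lower.
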